Safety 
• To assess the safety profile of the RSVt vaccine after each and any study intervention administration in pediatric participants.	Safety 
• Presence of any unsolicited systemic AEs reported in the 30 minutes after each study intervention administration• Presence of any solicited (ie, pre-listed in the participant's diary card [DC] and in the case report book [CRB]) administration site and systemic reactions within 21 days after each study intervention administration

Objectives	Endpoints
	
 • Presence of any unsolicited (spontaneously reported) AEs within 28 days after each study intervention administration • Presence of any AESIs within 28 days after each study intervention administration • Presence of any MAAEs within 28 days after each study intervention administration • Presence of any SAEs throughout the study
Transmission and virus shedding	Transmission and virus shedding

 • To describe the vaccine virus transmission in pediatric participants receiving placebo after the second study intervention administration 	
 • Presence of vaccine virus in D64 and D71 nasal swabs, detected by RSVt qRT-PCR in the pediatric participants receiving placebo
Exploratory	
    	    
	                           [figure not shown]Pediatric participants: Healthy infants / toddlers 6 to < 24 months of age in close contact with other infants / toddlers 6 to < 24 months of age who will participate in the studyAd-hoc close contact participants: Ad-hoc close contact children and adults who experience ARI in the 28 days following the administration of the study intervention to the close contact pediatric participant
Level and method of blinding	Observer-blind: 
Blinding for study intervention group assignment: participants, parents or LAR, outcome assessors, investigators, laboratory personnel, Sponsor study staffNo blinding for study staff who prepare and administer the study interventions
Study intervention assignment method	Pediatric participants will be screened for eligibility criteria at the time of inclusion and randomized to receive either RSVt vaccine or placebo in a 1:1 ratio. Randomization will be stratified by contact group (the household /group attended in daycare center) and by age group (< 12 months / ≥ 12 months)

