Number of participants	100 pediatric participants 6 to < 24 months of age
Intervention groups	Eligible pediatric participants will be randomized in a 1:1 ratio to receive 2 intranasal administrations (56 days apart) of either the RSVt vaccine or placebo at D01 and D57
Total duration of study participation	Approximately 8 months for each pediatric participant. The duration of the ad-hoc close contacts will be limited to the Illness Visit.
Countries	United States and Puerto Rico
Use of an Independent Data Monitoring Committee, Dose Escalation Committee, or similar review group	NO

VAD00014 study is planned to enroll a convenience sample of 100 children aged 6 to < 24 months (hereafter referred as pediatric participants) at least by pairs or larger groups of children, living in a context in which the probability of transmission is maximized, ie, group of children attending daycare centers, twins, and children living with siblings of similar age. The pediatric participants will be randomized to receive either the RSVt vaccine or placebo (the placebo group will allow to assess the transmissibility and safety of the RSVt vaccine in a blinded way).

VAD00014 study will be randomized, observer-blind, placebo-controlled, and will include 2 administrations, 56 days apart (ie, at Day (D)01 and D57). Pediatric participants will be randomized in 1:1 ratio and are planned to be enrolled in pairs or in small groups (ie, siblings or attending the same daycare center) to ensure that transmissibility from pediatric participants receiving the RSVt vaccine to pediatric participants receiving the placebo can be evaluated. Shedding, transmissibility, and genetic stability of the vaccine virus will be assessed through the collection of nasal swabs at regular intervals after each study intervention administration. As RSVt vaccine will be administered by intranasal route, vaccine virus shedding is then expected in the nose. Therefore, nasal swabs are commonly used for shedding assessment, especially in the infant population in which nasal washes are more invasive.

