4.2 Scientific Rationale for Study Design

Rationale for enrolling pediatric participants

It is expected that infants who already had RSV infection or who are seropositive present a lower virus shedding and thus a lower probability of vaccine virus transmission to their close contacts (23). In VAD00014 study, potential pediatric participants will not be screened based on their RSV baseline serostatus. Therefore, in order to maximize the probability of transmission during the study, enrolling a higher proportion of children aged 6 to 12 months may help to increase the proportion of seronegative participants and thereby increase the probability of transmission to pediatric participants receiving the placebo and / or to ad-hoc close contact participants. Some efforts will be made to enroll twins, to optimize the probability of transmission, and to limit the possible impact of age difference between the RSVt vaccine and placebo recipients. Stratification by age group could also be a way to control for the age distribution among RSVt vaccine and placebo recipients (eg, to ensure that for siblings, some younger and older children will receive RSVt vaccine).

Evaluation of Vaccine Virus Transmission

Transmission of the vaccine virus will be defined as presence of detected vaccine virus in the pediatric participants placebo-recipients and ad-hoc close contact participants, by RSVt qRT-PCR assay. Planned nasal swabs will be collected on all pediatric participants (ie, vaccinees and placebo recipients) on D01, D04, D08, D11, D15, D18, D22, D64, and D71. Nasal swabs will not be collected on D57 or D85 since vaccine virus shedding is not expected to last so long after the first administration and is expected to be lower after the second administration.

Based on an NIH study conducted with the same vaccine construct and on the same target population (20), it is expected that the probability of transmission from vaccinees to other persons will be higher when the virus shedding in the vaccinees is the highest (between 4 and 9 days after vaccine administration), so that nasal swabs will be collected regularly after the first administration to be able to detect vaccine virus. Vaccine virus shedding is expected to be lower after the second administration (8), justifying the collection of fewer nasal swabs after the second administration, and performing the interim analysis of the primary objective of transmission after the first dose.

[REDACTED]

Illness Visit(s)

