5.1 Inclusion Criteria

5.1.1 Inclusion Criteria

Participants are eligible for the study only if all of the following criteria are met:

AGE

I01. Aged 6 months to < 24 months on the day of inclusion¹

TYPE OF PARTICIPANT AND DISEASE CHARACTERISTICS

I02. Participants who are healthy as determined by medical evaluation including medical history.

I03. Born at full term of pregnancy (≥ 37 weeks) or born after a gestation period of 27 through 36 weeks and medically stable as assessed by the investigator, based on the following definition: “Medically stable” refers to the condition of premature infants who do not require significant medical support or ongoing management for debilitating disease and who have demonstrated a clinical course of sustained recovery by the time they receive the first dose of study intervention

I04. Attends a daycare facility at least 3 days per week and 4 hours per day at which the participant would be in a contact group/playroom of at least one other child 6 to < 24 months of age who will participate in this study or is a member of a household, which includes at least one other child 6 to < 24 months of age who will participate in this study

INFORMED CONSENT

I05. Informed consent form has been signed and dated by the parent(s) or other legally acceptable representative (and by an independent witness if required by local regulations)

OTHER INCLUSIONS

I06. Participant and parent/legally acceptable representative are able to attend all scheduled visits and to comply with all study procedures

¹ “6 months to < 24 months” means from the day of the 6 months after birth to the day before the 2nd birthday

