**Table 1.1: Design**

Type of design	Parallel, multi-center
Phase	II
Control method	Placebo-controlled
Study population	

Pediatric participants: Healthy infants / toddlers 6 to < 24 months of age in close contact with other infants / toddlers 6 to < 24 months of age who will participate in the study

Ad-hoc close contact participants: Ad-hoc close contact children and adults who experience acute respiratory illness (ARI) in the 28 days following the administration of the study intervention to the close contact pediatric participant

Level and method of blinding	Observer-blind: 

Blinding for study intervention group assignment: participants, parents or legally acceptable representative (LAR), outcome assessors, investigators, laboratory personnel, Sponsor study staff

No blinding for study staff who prepare and administer the study interventions

Study intervention assignment method	Pediatric participants will be screened for eligibility criteria at the time of inclusion and randomized to receive either RSVt vaccine or placebo in a 1:1 ratio. Randomization will be stratified by contact group (the household /group attended in daycare center) and by age group (< 12 months / ≥ 12 months)

Number of participants	100 pediatric participants 6 to < 24 months of age
Intervention groups	Eligible pediatric participants will be randomized in a 1:1 ratio to receive 2 intranasal administrations (56 days apart) of either the RSVt vaccine or placebo at D01 and D57
Total duration of study participation	Approximately 8 months for each pediatric participant. The duration of the ad-hoc close contacts will be limited to the Illness Visit.
Countries	United States and Puerto Rico
Use of an Independent Data Monitoring Committee, Dose Escalation Committee, or similar review group	NO

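### Randomization stratified by contact group and age, with no rule that both arms occur in each group, can leave placebo children without a vaccinee in their group, yet they still count in the transmission percentage

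*Protocol*

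**What the plan says.** The assignment method in Protocol Section 4.1 (Table 4.1) names two stratification factors: "Randomization will be stratified by contact group (the household /group attended in daycare center) and by age group" (under 12 months, or 12 months and older). SAP Table 1.1 repeats them. Contact group here means the individual household or daycare group, not the type of setting: Protocol Section 6.3.1 gives each one an identifier within the participant number, and SAP Appendix 2 treats it as the unit of transmission.

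The smallest group is a pair. Section 4.1 plans to enroll "at least by pairs or larger groups of children", and under inclusion criterion I04 a child qualifies who "is a member of a household, which includes at least one other child 6 to < 24 months of age", provided that the other child also participates. Nothing requires the two to be in the same age stratum.

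Section 4.1 gives the purpose of enrolling pairs and small groups: "to ensure that transmissibility from pediatric participants receiving the RSVt vaccine to pediatric participants receiving the placebo can be evaluated". Section 4.2 gives a separate purpose for the age factor: "Stratification by age group could also be a way to control for the age distribution among RSVt vaccine and placebo recipients", so that among siblings both younger and older children receive vaccine.

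Neither document states a block size, says how the two factors combine, or requires both arms in each contact group. Section 6.3.1 says only that the IRT supplies the assignment.

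The primary transmission percentage (Protocol Section 9.3.2, SAP Section 3.4.2.1) is taken over placebo recipients in the SafAS and the PPAS. No PPAS exclusion (Protocol Section 9.2, SAP Section 3.3) removes a placebo child whose group holds no vaccinee.

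**The concern.** Enrollment in pairs serves its purpose only if the pair contains a possible source and a possible recipient. Crossing contact group with age can separate the two children of a pair into different strata, and then nothing links their allocations.

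A both-placebo pair contributes two children with no vaccinee in their group, and both count in the primary denominator. A both-RSVt pair contributes no placebo child. The first kind pulls the reported transmission percentage down, and the second wastes a pair for vaccinee-to-placebo spread. The error is towards reassurance, in a study whose rationale (Protocol Section 2.1) is to show that a large-scale study can be conducted safely.

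**Working it through.** **The plan's own figure.** Protocol Section 9.5 and SAP Section 3.2 give 100 children, 50 per arm, on feasibility grounds with no calculation. At 1:1, 100/2 = 50. There is nothing further to reproduce.

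**Step 1: two children in different age strata.** Each takes the first place on a separate list, so P(same arm) = 0.5 × 0.5 + 0.5 × 0.5 = 0.50, made up of 25% both placebo and 25% both RSVt. Block size does not enter. Simulation with 200,000 draws at each of block sizes 2, 4, 6 and 8 gave 0.500 to 0.501.

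**Step 2: two children in the same stratum and block of size b.** P(same arm) = (b/2 − 1)/(b − 1).

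| Block size | P(same arm) |
|---|---|
| 2 | 0 |
| 4 | 1/3 |
| 6 | 2/5 |
| 8 | 3/7 |

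Same-age pairs, including twins, are therefore always split only with blocks of 2.

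**Step 3: three or more children.** With two age strata, at least two children share a stratum. With blocks of 2 those two get opposite arms, so the group always holds both. With blocks of 4, a group of two plus one is all one arm with probability 1/3 × 1/2 = 1/6. A group of two plus two is all one arm with probability 2 × 1/6 × 1/6 = 1/18.

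**Step 4: how common straddling pairs are.** The documents do not say. Two assumptions give an idea:
- Unrelated daycare pairs, ages uniform on 6 to 24 months: one third are under 12 months, so 2 × 1/3 × 2/3 = 0.44 straddle.
- Non-twin siblings both aged 6 to <24 months, at least 9 months between births, uniform over feasible gaps and ages: 36/40.5 = 0.89 straddle.

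Twins never straddle.

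**Step 5: effect on the percentage.** Assume that all 100 children come as 50 pairs, that same-age pairs use blocks of 2, that a share f of pairs straddles 12 months, and that only placebo children with a vaccinee in their group can become positive. The expected number of both-placebo pairs is 50f/4, which is 25f placebo children, or f/2 of the 50. The observed percentage is the true one times (1 − f/2). The upper limit for zero detections among n children is 1 − 0.025^(1/n).

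| f | Placebo children with no source in group | True 10% reads | Expected exposed n | Upper 95% limit for 0/n |
|---|---|---|---|---|
| 0 | 0% | 10.0% | 50 | 7.1% |
| 0.25 | 12.5% | 8.8% | 43.75 | 8.1% |
| 0.50 | 25% | 7.5% | 37.5 | 9.4% |
| 1.00 | 50% | 5.0% | 25 | 13.7% |

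These are expected values. With 25 straddling pairs, the number sharing an arm has a 95% range of 8 to 17.

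**Step 6: the models in SAP Appendix 2.** For a group with no vaccinee, I_j = 0.
- Reed-Frost: with X_j = 0 the factor is q^(0 × S_j) = 1, so the group adds nothing.
- Greenwood: the factor is q^(S_j). The estimate is ΣX_j/ΣS_j, so these children stay in its denominator and it is diluted by the same (1 − f/2).

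**The case against.** **The mechanism is not documented.** The text names two factors but does not say that they are fully crossed, and it does not exclude minimization or a forced split within the group. Over possible mechanisms, the chance that a straddling pair shares an arm runs from 0% to 50%. This stands as a limit on certainty. It does not remove the point, because crossed strata are the ordinary meaning of the wording and nothing in either document states another rule.

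**Most groups may be protected.** Recruitment emphasizes twins and includes daycare groups. With blocks of 2, twins and any group of three or more always hold both arms. This stands. A reader might infer from the sibling arithmetic that about half of all pairs are lost, or that reported transmission is halved. That would need every child to be in a two-child group straddling 12 months, which is not the recruitment described.

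**Both-RSVt pairs are not useless.** A reader might infer that they can show no transmission at all. SAP Section 4.2.1 also counts detection in ad-hoc close contacts, who are swabbed when ill, and these pairs still inform shedding, safety and immunogenicity. What they cannot show is spread to a placebo child in the pair.

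**The aim is at study level.** Section 4.1 does not promise that each pair is split, and even at f = 1 an expected 25 pairs remain informative. So the documents do not support saying that transmission cannot be evaluated. The endpoint is descriptive and Reed-Frost conditions on I_j. But the primary percentage and the Greenwood estimate have no such protection, and a descriptive estimate can still be biased.

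**Conclusion.** The point holds. As written, the allocation rule does not secure both arms in each contact group, and the primary analysis does not allow for groups without a vaccinee. On the crossed reading, half of two-child groups straddling 12 months are expected to share an arm, whatever the block size.

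The overall size is a range, because neither the straddling share nor the block scheme is given. Under the all-pairs assumption with blocks of 2 for same-age pairs, 12.5% to 50% of placebo children would have no source in their group as the straddling share runs from 25% to 100%. The top of that range is an upper bound that the planned enrollment makes unlikely. Larger blocks would add some loss among same-age pairs; groups of three or more would reduce it.

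A reader might also conclude that the primary denominator should be replaced. The documents do not support going that far: the sponsor is unblinded at the interim analyses (Protocol Section 9.4, SAP Section 3.5), so adding a restricted analysis beside the planned one is sounder than substituting it.

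**What to change.** 1. **Allocation.** For contact groups not yet randomized, allocate 1:1 within the contact group so that each has at least one child per arm. In mixed-age groups, balance across groups whether the younger or the older child receives RSVt, which keeps the aim of Protocol Section 4.2. State the block scheme, and align Protocol Table 4.1 and SAP Table 1.1. If the IRT already forces this split, correct the text to say so.
2. **Analysis.** In the SAP, keep the planned percentage among all placebo recipients. Add the transmission percentage with its 95% CI among placebo children whose contact group has at least one RSVt recipient, and list the placebo children in groups without one. This restriction depends on allocation, not on outcome. Drop groups with I_j = 0 from the Greenwood likelihood.

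**Cost.** An IRT specification change, which helps only groups still to be randomized (their number is not in the documents), plus wording and one extra table and listing. The downside is to blinding: in a forced-split pair, breaking one child's code reveals the other's, whereas Protocol Section 6.3.2 wants code-breaking confined to the affected child. The amended text should acknowledge this.

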4.2 Scientific Rationale for Study Design

Rationale for enrolling pediatric participants

It is expected that infants who already had RSV infection or who are seropositive present a lower virus shedding and thus a lower probability of vaccine virus transmission to their close contacts (23). In VAD00014 study, potential pediatric participants will not be screened based on their RSV baseline serostatus. Therefore, in order to maximize the probability of transmission during the study, enrolling a higher proportion of children aged 6 to 12 months may help to increase the proportion of seronegative participants and thereby increase the probability of transmission to pediatric participants receiving the placebo and / or to ad-hoc close contact participants. Some efforts will be made to enroll twins, to optimize the probability of transmission, and to limit the possible impact of age difference between the RSVt vaccine and placebo recipients. Stratification by age group could also be a way to control for the age distribution among RSVt vaccine and placebo recipients (eg, to ensure that for siblings, some younger and older children will receive RSVt vaccine).

Evaluation of Vaccine Virus Transmission

Transmission of the vaccine virus will be defined as presence of detected vaccine virus in the pediatric participants placebo-recipients and ad-hoc close contact participants, by RSVt qRT-PCR assay. Planned nasal swabs will be collected on all pediatric participants (ie, vaccinees and placebo recipients) on D01, D04, D08, D11, D15, D18, D22, D64, and D71. Nasal swabs will not be collected on D57 or D85 since vaccine virus shedding is not expected to last so long after the first administration and is expected to be lower after the second administration.

Based on an NIH study conducted with the same vaccine construct and on the same target population (20), it is expected that the probability of transmission from vaccinees to other persons will be higher when the virus shedding in the vaccinees is the highest (between 4 and 9 days after vaccine administration), so that nasal swabs will be collected regularly after the first administration to be able to detect vaccine virus. Vaccine virus shedding is expected to be lower after the second administration (8), justifying the collection of fewer nasal swabs after the second administration, and performing the interim analysis of the primary objective of transmission after the first dose.

[REDACTED]

Illness Visit(s)

For any pediatric participants presenting clinical symptoms of ARI during the intervention phase (D1 to D85), an additional nasal swab may be collected to identify potential WT RSV infection with Multiplex RT-PCR. Some of the regular nasal swabs from symptomatic children in which no vaccine virus was detected may also be tested for WT RSV strain. If ARI is diagnosed < 2 days before or after a scheduled nasal swab, then the planned nasal swab will be used for WT RT-PCR testing. The ad-hoc close contact participants with any clinical symptoms of ARI within 28 days after study intervention administration of the close contact pediatric participant should have an illness visit.

Consideration of the RSV Season

The VAD00014 study is planned to start during Quarter (Q)4 2022, regardless of the actual start of the RSV season. In the Northern Hemisphere, the RSV season usually begins in late Q3 or early Q4 and lasts about 5 months. However, due to the increased variability in the RSV epidemiology since the beginning of the SARS-CoV-2 pandemic, it is difficult to evaluate the extent to which the RSV season will impact the clinical study. To mitigate the impact of the RSV season during the study, ARI will be followed up to 28 days after the second study intervention administration for all pediatric participants. Baseline blood sample will be used as an indication of possible previous RSV exposure.

Non-exclusion of pregnant women participants

Ad-hoc close contact participants can include pregnant females as they will only provide nasal swabs and will not receive any study intervention. Thus, VAD00014 study can be considered a safety surveillance study for the ad-hoc close contact participants and therefore pregnant women are not excluded from participating in the study.

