†‡ Illness Visits: Additional nasal swab specimens for the detection of RSV and respiratory pathogens" (including COVID-19) will also be collected from pediatric participants in case of acute respiratory illness. All the nasal swab specimens will be collected in the recommended viral transport media tube and will be stored between -60°C and -80°C until ready to ship.

Table 1.2: Schedule of activities for ad-hoc close contact participants

Phase II Study, at least 1 Unplanned Illness Visit, at least 1 Unplanned Nasal Swab, Duration is limited to the Illness Visit(s)

Visit (V) / Contact*	Collection of information in the CRF	Illness Visit(s)
Study timelines - Days(D)		Not applicable
Visit Interval		ARI** symptoms during the 28 days following any administration of the study intervention to the close contact pediatric participant
Time windows (days)		Not applicable
Informed consent†	X	X
Collection of demographic data†	X	X
Allocation of participant number†	X	X
Nasal swab (NS)‡	X	UN0001 to UN000X§
Collection of End of Study status	X	At the end of the study intervention phase for the pediatric participant in close contact to ad-hoc participant

Abbreviations: CRF, case report form; ARI, acute respiratory illness

* Additional unscheduled visits may be performed for safety reasons; information will be reported in the source documents.

† To be collected during the first illness visit.

‡ Illness Visits: All the nasal swab specimens will be collected in the recommended viral transport media tube and will be stored between -60°C and -80°C until ready to ship.

§ Ad-hoc close contact participants will provide a nasal swab sample for detection of vaccine virus transmission. The same nasal swab specimen may also be tested for respiratory pathogens (including COVID-19).

** Acute respiratory illness includes upper and lower respiratory illness.

2 Introduction

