7.1 Discontinuation of Study Intervention

7.1.1 Temporary Contraindications

Should a participant experience one of the conditions listed below, the investigator will postpone further vaccination until the condition is resolved. Postponement must still be within the timeframe for vaccination indicated in the SoA.

If the postponement occurs out of the timeframe for vaccination, the participant will be permanently discontinued from study intervention but will continue to be followed for safety

TCI01: Any acute febrile illness in the past 48 hours that according to investigator judgment is significant enough to interfere with successful inoculation on the day of vaccination. A prospective participant should not be included in the study until the condition has resolved or the febrile event has subsided

TCI02: Receipt or planned receipt of any of the following vaccines prior to or after the first study intervention administration:

- any influenza vaccine within 7 days prior to and after, or
- any COVID-19 or inactivated vaccine or live-attenuated rotavirus vaccine within 14 days prior to and after, or
- any live vaccine, other than rotavirus vaccine, within 28 days prior to and after

Temporary intervention discontinuation may be considered by the investigator because of suspected AEs. For all temporary intervention discontinuations, duration should be recorded by the investigator in the source documents.

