### 3.4.3.3 Vaccine virus transmission

Presence of vaccine virus detected by RSVt qRT-PCR in nasal swabs after the second vaccination (D64 and D71) will be summarized in pediatric participants receiving placebo with 95% CIs:

- Number and percentage of participants with vaccine virus detected at each timepoint
- Number and percentage of participants with vaccine virus detected in at least one nasal swab

Transmissibility analyses will be performed on the SafAS. Vaccine virus transmission is defined in [Section 4.2.1](#).

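### Placebo children's swabs are timed and analysed from their own doses, so a contact's later dosing can cut detection of transmission, mainly after dose 2

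*Protocol*

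**What the plan says.** **Swab timing.** Protocol 4.2 states: "Planned nasal swabs will be collected on all pediatric participants (ie, vaccinees and placebo recipients) on D01, D04, D08", and so on to D22, then D64 and D71. In the Schedule of Activities (Protocol 1.3, repeated in SAP Table 1.2), V02 to V07 are counted from the child's own V01. V08 is the child's own V01 + 56 days with a window of +7. V09 and V10 are the child's own V08 + 7 and + 14 days, each with a window of +1. One child's second dose may be delayed within this limit: "Postponement must still be within the timeframe for vaccination indicated in the SoA" (Protocol 7.1.1).

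**What drives exposure.** Protocol 4.2 expects transmission to be likeliest "when the virus shedding in the vaccinees is the highest (between 4 and 9 days after vaccine administration").

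**What links children in a group.** Participants "are planned to be enrolled in pairs or in small groups (ie, siblings or attending the same daycare center) to ensure that transmissibility" from vaccinees to placebo recipients can be evaluated (Protocol 4.1). Criterion I04 asks for "at least one other child 6 to < 24 months of age who will participate in this study". Randomization is stratified by contact group. None of these fixes a shared dosing date or a largest gap. For ad-hoc contacts, by contrast, follow-up is tied to the dosed child: an illness visit is triggered by acute respiratory "symptoms during the 28 days following any administration of the study intervention to the close contact pediatric participant".

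**Analysis.** SAP 3.4.2.1 and 3.4.3.3 summarise placebo children by their own visit days, for example "Presence of vaccine virus detected by RSVt qRT-PCR in nasal swabs after the second vaccination (D64 and D71"). The per-protocol rule of at least 4 valid swabs (SAP 3.3) uses the child's own D08 to D22. The chain-binomial model in SAP Appendix 2 uses counts per contact group and no dates.

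**The concern.** A placebo swab is informative about transmission according to how long after the vaccinee's dose it is taken. The plan records and tabulates a different quantity, days since the placebo child's own dose. The two agree only when children of a group are dosed together.

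If the vaccinee is dosed later, the placebo child's last swab may come before an infection acquired late in the shedding period could show. That child stays in the denominator as a full negative, and no rule in the SAP identifies the case. The error runs towards low transmission. The dose 1 results are to be shared with Health Authorities before Phase III (SAP 3.5), so readers need to know how much useful observation lies behind a low rate.

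**Working it through.** **Reproducing the schedule.** Day label = 1 + offset from V01. V07 = 1 + 21 = D22; V08 = 1 + 56 = D57; V09 = 57 + 7 = D64; V10 = 57 + 14 = D71. All match the plan.

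**Dose 2.** Let g = vaccinee's V08 date minus placebo child's V08 date. The placebo swabs then fall on vaccinee days 7 - g and 14 - g, with the vaccinee's dose as day 0. With V01 on the same day, the V08 window alone lets g run from -7 to +7.

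| g | Nominal swabs, vaccinee day | Swabs after day 9 |
|---|---|---|
| 0 | 7, 14 | 1 |
| 3 | 4, 11 | 1 |
| 4 | 3, 10 | 1 |
| 5 | 2, 9 | 0 |
| 6 | 1, 8 | 0 |
| 7 | 0, 7 | 0 |

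Assume the two V08 dates are independent and uniform over the 8 permitted days (64 combinations). Gaps of 5, 6 and 7 arise in 3, 2 and 1 combinations, so P(g ≥ 5) = 6/64 = 9.4%. If V10 is taken on its +1 day, the last swab is on day 15 - g, so a swab after day 9 is lacking only at g ≥ 6: 3/64 = 4.7%.

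**Dose 1.** Let L = days by which the placebo child leads the first vaccinee. Nominal swabs are at offsets 0, 3, 7, 10, 14, 17 and 21, so the last is on vaccinee day 21 - L.

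- L = 7: swabs on days 7, 10 and 14 remain from day 4 on.
- L = 12: the last swab is on day 9.
- L = 13: swabs on days 4 and 8, both in the peak. With the +1 day window the last is on day 9 at the latest, so none falls after day 9.
- L = 18: the last swab is on day 3, so none falls from day 4 on.

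**Allowing for the contact's own infection.** Assumptions, not in the documents: infection equally likely on vaccinee days 4 to 9, a delay of 2 to 5 days to detectability, and 3 to 10 days detectable. Share of infected contacts caught by a scheduled swab:

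| Dose | Offset | Share caught |
|---|---|---|
| 2 | g = 0 | 33%-100% |
| 2 | g = 5 | 17%-67% |
| 2 | g = 7 | 0%-33% |
| 2 | g = -7 | 0%-100% |
| 1 | L = 0 or 7 | 83%-100% |
| 1 | L = 14 | 0%-33% |
| 1 | L = 18 | 0% |

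**Effect on the interval.** With 0 events in n, the Clopper-Pearson upper 95% limit is 1 - 0.025^(1/n). For n = 50 it is 7.1%. Under the uniform assumption, with one vaccinee per placebo child, 50 × 6/64 ≈ 5 children have g ≥ 5. Removing them all gives n = 45 and 1 - 0.025^(1/45) = 7.9%. If only 40 or 30 children were usefully swabbed (assumed), the limit is 8.8% or 11.6%.

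**The case against.** **Group enrolment.** Enrolment in pairs or small groups is planned precisely so that transmission can be evaluated, and twins or siblings will often attend together. Independent uniform V08 dates are therefore probably pessimistic. In a daycare group with several vaccinees, a placebo child is poorly covered only if all of them are dosed late. This stands: 9.4% illustrates what the window permits and is not a forecast.

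**Importance of dose 2.** Dose 2 transmission is secondary and descriptive, and the protocol expects lower shedding then, "justifying the collection of fewer nasal swabs after the second administration". This limits the stakes. It also means there are only two swabs, so little slack.

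**Backstop.** An illness swab may be taken from a pediatric participant with acute respiratory symptoms up to D85. This helps in part, but it needs symptoms and is aimed at wild-type RSV.

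**Unavailable text.** Figure 1 and parts of Protocol 4.2 and 8.1.2 cannot be read. A same-date rule there cannot be excluded.

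Three stronger readings are tempting and not supported:

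- That the swabs could not have detected transmission at all. At g = 5 to 7 one swab still falls on vaccinee day 9, 8 or 7, and at a dose 1 lead of 13 days two fall in the peak. Sensitivity is reduced, not lost.
- That the primary dose 1 rate is compromised. Six post-dose swabs absorb about a week's offset, and larger gaps would depart from the planned group enrolment, although nothing readable forbids them.
- That every pair without a swab in days 4-9 is a missed pair (15 to 19 of 64 after dose 2). Most of those are pairs with the vaccinee dosed earlier, where the swabs may still catch a lagged infection in the contact.

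**Conclusion.** The point holds in a limited form. On the readable text, nothing aligns a placebo child's swabs or their analysis with the vaccinee's dose. For the secondary dose 2 rate, this follows from the schedule itself. A gap of 5 to 7 days leaves no nominal swab after the peak, and such children are still counted as full negatives. That is 9.4% of pairs under the uniform assumption, or 4.7% if V10 is always taken on its +1 day. The bias is downwards; on these figures the upper limit for zero events moves from 7.1% to at most about 7.9%.

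For the primary dose 1 rate the effect is conditional. It needs a placebo child who starts about 13 or more days before every vaccinee in the group, and detection by scheduled swab is essentially gone only at 18 or more days. The documents neither require nor exclude such starts. The actual size can be read from the trial's own dates, which is the reason to plan the check now.

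**What to change.** In SAP 3.4.2.1, 3.4.3.3 and 4.2.1:

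1. For each placebo swab, derive the days since the first RSVt administration in that contact group for that dose. Dosing and swab dates are already collected, and the contact group is coded in the participant number (Protocol 6.3.1).
2. Summarise transmission on this clock beside the visit-day tables.
3. Show separately, and exclude in a sensitivity analysis, placebo children with no valid swab after day 9 on this clock, or with no vaccinee in the group who received that dose.

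No change to the visit schedule is proposed. Timing the post-dose-2 swabs from the latest V08 in the group may look attractive. However, it would move the swabs of a vaccinee dosed 7 days earlier to that child's own days 14 and 21, or later if V01 dates also differ. D64 and D71 shedding is a primary endpoint, so this would trade primary data for a secondary one.

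Cost: one derived variable and one or two tables. The sensitivity analysis has a smaller denominator and a wider interval.
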